8.2.5 Other Screening Assessments

Other screening assessments referred to in the SoA ([Table 1](#), [Table 2](#) and [Table 3](#)) are shown below.

Viral serology (screening only)

[Part A/Part B/Part C]

HIV I	Hepatitis B surface antigen (HBsAg)
HIV II	Hepatitis C virus antibody

8.2.6 Injection Site Reactions

Injection site reactions should be reported using standard AE collection criteria. Details regarding the ISRs will be collected in a specific eCRF page.

8.3 Adverse Events and Serious Adverse Events

The PI is responsible for ensuring that all staff involved in the study are familiar with the content of this section

The definitions of an AE or SAE can be found in [Appendix B](#).

Adverse events will be reported by the participant (or, when appropriate, by a caregiver, surrogate, or the participant's legally authorised representative).

The investigator and any designees are responsible for detecting, documenting, and recording events that meet the definition of an AE.

8.3.1 Time Period and Frequency for Collecting AE and SAE Information

Adverse events will be collected from time of first dose throughout the treatment period and including the follow-up period.

SAEs will be recorded from the time of signing of the informed consent form.

If the Investigator becomes aware of an SAE with a suspected causal relationship to the study intervention that occurs after the end of the clinical study in a participant treated by him or her, the Investigator shall, without undue delay, report the SAE to the sponsor.

8.3.2 Follow-up of AEs and SAEs

Any AEs that are unresolved at the participant's last AE assessment in the study are followed up by the Investigator for as long as medically indicated, but without further recording in the eCRF. AstraZeneca retains the right to request additional information for any participant with ongoing AE(s)/SAE(s) at the end of the study, if judged necessary.

Adverse event variables

The following variables will be collected for each AE;

- AE (verbatim)
- The date and time when the AE started and stopped
- Maximum intensity
- Whether the AE is serious or not
- Investigator causality rating against the Investigational Product(s) (yes or no)
- Action taken with regard to Investigational Product(s)
- AE caused participant's withdrawal from study (yes or no)
- Outcome
- Whether the AE is an injection site reaction or not

In addition, the following variables will be collected for SAEs:

- Date AE met criteria for SAE
- Date investigator became aware of SAE
- AE is serious due to
- Date of hospitalisation
- Date of discharge
- Probable cause of death

- Date of death
- Autopsy performed
- Causality assessment in relation to study procedure(s)
- Causality assessment to other medication
- Description of AE

8.3.3 Causality Collection

The investigator should assess causal relationship between Investigational Product and each AE, and answer ‘yes’ or ‘no’ to the question ‘Do you consider that there is a reasonable possibility that the event may have been caused by the investigational product?’

For SAEs, causal relationship should also be assessed for other medication and study procedures. Note that for SAEs that could be associated with any study procedure the causal relationship is implied as ‘yes’.

A guide to the interpretation of the causality question is found in [Appendix B](#) to the Clinical Study Protocol.

8.3.4 Adverse Events Based on Signs and Symptoms

All AEs spontaneously reported by the participant or reported in response to the open question from the study site staff: ‘Have you had any health problems since the previous visit/you were last asked?’, or revealed by observation will be collected and recorded in the eCRF. When collecting AEs, the recording of diagnoses is preferred (when possible) to recording a list of signs and symptoms. However, if a diagnosis is known and there are other signs or symptoms that are not generally part of the diagnosis, the diagnosis and each sign or symptom will be recorded separately.

8.3.5 Adverse Events Based on Examinations and Tests

The results from the Clinical Study Protocol mandated laboratory tests and vital signs will be summarised in the Clinical Study Report (CSR).

Deterioration as compared to baseline in protocol-mandated laboratory values and vital signs should therefore only be reported as AEs if they fulfil any of the SAE criteria, are the reason for discontinuation of treatment with the investigational product or are considered to be clinically relevant as judged by the investigator (which may include but not limited to consideration as to whether treatment or non-planned visits were required or other action was taken with the study intervention, eg, dose adjustment or drug interruption).

If deterioration in a laboratory value/vital sign is associated with clinical signs and symptoms, the sign or symptom will be reported as an AE and the associated laboratory result/vital sign

will be considered as additional information. Wherever possible the reporting investigator uses the clinical, rather than the laboratory term (eg, anaemia versus low haemoglobin value). In the absence of clinical signs or symptoms, clinically relevant deteriorations in non-mandated parameters should be reported as AE(s).

Deterioration of a laboratory value, which is unequivocally due to disease progression, should not be reported as an AE/SAE.

Any new or aggravated clinically relevant abnormal medical finding at a physical examination as compared with the baseline assessment will be reported as an AE unless unequivocally related to the disease under study.

8.3.6 Hy's Law

Cases where a participant shows elevations in liver biochemistry may require further evaluation and occurrences of AST or ALT $\geq 3 \times$ ULN together with total bilirubin $\geq 2 \times$ ULN may need to be reported as SAEs. Please refer to [Appendix E](#) for further instruction on cases of increases in liver biochemistry and evaluation of Hy's Law.

8.3.7 Reporting of Serious Adverse Events

All SAEs have to be reported, whether or not considered causally related to the investigational product, or to the study procedure(s). All SAEs will be recorded in the eCRF.

If any SAE occurs in the course of the study, investigators or other site personnel will inform the appropriate AstraZeneca representatives within one day ie, immediately but **no later than 24 hours** of when he or she becomes aware of it.

The designated AstraZeneca representative will work with the investigator to ensure that all the necessary information is provided to the AstraZeneca Patient Safety data entry site **within one calendar day** of initial receipt for fatal and life-threatening events **and within 5 calendar days** of initial receipt for all other SAEs.

For fatal or life-threatening AEs where important or relevant information is missing, active follow-up will be undertaken immediately. Investigators or other site personnel will inform AstraZeneca representatives of any follow-up information on a previously reported SAE within one calendar day, ie, immediately but **no later than 24 hours** of when he or she becomes aware of it.

Once the investigators or other site personnel indicate an AE is serious in the Electronic Data Capture (EDC) system, an automated email alert is sent to the designated AstraZeneca representative.

If the EDC system is not available, then the investigator or other study site staff reports a SAE

to the appropriate AstraZeneca representative by telephone.

The AstraZeneca representative will advise the investigator/study site staff how to proceed.

The reference document for definition of expectedness/listedness is the Investigator's Brochure (IB) for the AstraZeneca drug.

8.3.8 Pregnancy

All pregnancies and outcomes of pregnancy should be reported to AstraZeneca except for:

- If the pregnancy is discovered before the study participant has received any study intervention

8.3.8.1 Maternal Exposure

Women of childbearing potential are not allowed to be included in this study. Should a pregnancy still occur, the investigational product should be discontinued immediately and the pregnancy reported to AstraZeneca.

Pregnancy itself is not regarded as an adverse event unless there is a suspicion that the investigational product under study may have interfered with the effectiveness of a contraceptive medication. Congenital anomalies/birth defects and spontaneous miscarriages should be reported and handled as SAEs. Elective abortions without complications should not be handled as AEs. The outcome of all pregnancies (spontaneous miscarriage, elective termination, ectopic pregnancy, normal birth or congenital anomaly/birth defect) should be followed up and documented even if the participant was discontinued from the study.

If any pregnancy occurs, then the investigator or other site personnel informs the appropriate AstraZeneca representatives within **1 day**, ie, immediately but **no later than 24 hours** of when he or she becomes aware of it.

The designated AstraZeneca representative works with the investigator to ensure that all relevant information is provided to the AstraZeneca Patient Safety data entry site **within 1 or 5 calendar days** for SAEs (see Section [8.3.7](#)) and **within 30 days** for all other pregnancies.

The same timelines apply when outcome information is available.

The PREGREP module in the eCRF is used to report the pregnancy.

8.3.8.2 Paternal Exposure

Male participants should refrain from fathering a child during the study and for 3 months following the final follow-up visit (see also Section [5.3.4](#)). In case of pregnancy of the partner of a male participants, the partner's pregnancy should be reported on the pregnancy form (consent from the partner must be obtained before the pregnancy form is completed) following

the same timeframe and routing as described for any participant's pregnancy. Pregnancy of the participant's partner is not considered to be an AE. The pregnancy will also be followed up, and the outcome of the pregnancy (spontaneous miscarriage, elective termination, ectopic pregnancy, normal birth, or congenital anomaly/birth defect) should, if possible, be obtained and documented.

8.3.9 Medication Error

If a medication error occurs in the course of the study, then the investigator or other site personnel informs the appropriate AstraZeneca representatives within **1 day**, ie, immediately but **no later than 24 hours** of when he or she becomes aware of it.

The designated AstraZeneca representative works with the investigator to ensure that all relevant information is completed within **1** (Initial Fatal/Life-Threatening or follow up Fatal/Life-Threatening) **or 5** (other serious initial and follow up) **calendar days** if there is an SAE associated with the medication error (see Section [8.3.7](#)) and **within 30 days** for all other medication errors.

The definition of a Medication Error can be found in Appendix [B 4](#).

8.4 Overdose

For this study, any dose of AZD8233 greater than the planned dose will be considered an overdose.

In cases of known or suspected overdose, symptomatic treatment and monitoring of vital functions should be performed according to routine clinical practice.

- An overdose with associated AEs is recorded as the AE diagnosis/symptoms on the relevant AE modules in the eCRF and on the Overdose eCRF module.
- An overdose without associated symptoms is only reported on the Overdose eCRF module.

If an overdose on an AstraZeneca study intervention occurs in the course of the study, the investigator or other site personnel inform appropriate AstraZeneca representatives immediately, but **no later than 24 hours** of when he or she becomes aware of it.

The designated AstraZeneca representative works with the investigator to ensure that all relevant information is provided to the AstraZeneca Patient Safety data entry site **within one or 5 calendar days** for overdoses associated with an SAE (see section [8.3.7](#)) and **within 30 days** for all other overdoses.

8.5 Human Biological Samples

Instructions for the collection and handling of biological samples will be provided in the study specific laboratory manual. Samples should be stored in a secure storage space with adequate measures to protect confidentiality. For further details on Handling of Human Biological Samples see [Appendix C](#).

Samples will be stored for a maximum of 15 years from the date of the issue of the CSR in line with consent and local requirements, after which they will be destroyed/repatriated.

- Pharmacokinetic (PK) samples will be disposed of after the Bioanalytical Report finalization or 6 months after issuance of the draft Bioanalytical Report (whichever is earlier), unless consented for future analyses.
 - Pharmacokinetic samples may be disposed of or anonymised by pooling. Additional analyses may be conducted on the anonymised, pooled pharmacokinetic samples to further evaluate and validate the analytical method. Any results from such analyses may be reported separately from the CSR.
- Remaining anti-drug antibody (ADA) sample aliquots will be retained at AstraZeneca or its designee for a maximum of 15 years following issue of the CSR. Additional use includes but is not limited to further characterization of any ADAs, confirmation and/or requalification of the assay as well as additional assay development work. The results from future analysis will not be reported in the CSR.

8.5.1 Pharmacokinetics

[Part A/Part C]

Blood samples for the determination of plasma concentrations of AZD8233 and AZD8233 total full lengths ASOs will be collected for each treatment period as specified in the SoA. The concentration levels of AZD8233 total full lengths ASOs will be used to assess all the primary PK-parameters. Blood samples for a potential exploration of the plasma concentrations levels of unchanged AZD8233 will also collected as specified in the SoA.

Urine samples for the determination of urine concentrations of AZD8233 total full length ASOs will be collected for each treatment period as specified in the SoA.

Samples will be collected, handled, labelled, stored and shipped as detailed in the Laboratory Manual.

[Part B]

Plasma samples will be collected for measurement of plasma concentrations of total full-length ASOs of AZD8233 as specified in the SoA.

Samples may be collected at additional time points during the study if warranted and agreed upon between the investigator and the sponsor, eg, for safety reasons. The timing of sampling

may be altered during the course of the study based on newly available data (eg, to obtain data closer to the time of peak or trough matrix concentrations) to ensure appropriate monitoring.

Plasma samples will be used to analyse the PK of AZD8233. Samples collected for this PK purpose may also be used to evaluate safety and efficacy aspects related to concerns arising during or after the study.

Samples will be collected, labelled, stored, and shipped as detailed in the Laboratory Manual.

8.5.1.1 Determination of Drug Concentration

[Part A/Part C]

Blood and urine samples will be analyzed by Labcorp on behalf of AstraZeneca Research, using validated (plasma)/qualified (urine) assays, for determination of AZD8233 and AZD8233 total full lengths ASOs concentrations in plasma and AZD8233 total full lengths ASOs concentrations in urine. Full details of the analytical methods used will be described in a separate bioanalytical report.

[Part B]

Blood samples for determination of AZD8233 total full lengths ASOs concentrations in plasma will be analyzed by Labcorp on behalf of AstraZeneca Research, using validated (plasma)/qualified (urine) assays. Full details of the analytical methods used will be described in a separate bioanalytical report.

[Part A/Part B/Part C]

Placebo samples will not be analyzed, unless there is a need to confirm that correct treatment has been given to study participants.

Incurred sample reproducibility analysis, if any, will be performed alongside the bioanalysis of the test samples. The results from the evaluation will not be reported in the CSR but separately in a Bioanalytical Report. In the event of safety concerns, blood samples collected for PK or PD analysis may be used for safety laboratory analysis at the discretion of the Investigator.

8.5.2 Immunogenicity Assessments

Blood samples for immunogenicity assessments (ADA) will be collected according to the SoA ([Table 1](#), [Table 2](#) and [Table 3](#)).

The presence or absence of ADAs will be determined in the plasma samples using a validated bioanalytical method. A tiered testing scheme will be employed, with the first step being screening. Samples found positive in the screening step will be tested in the confirmatory step.

Samples confirmed positive for ADA in the confirmatory step will undergo endpoint titer determination. Full details of the analytical method and analyses performed will be described in a separate bioanalytical report.

ADA samples may also be further tested for characterisation of the ADA response. Study results may be reported independently to ADA follow-up.

Samples will be collected, labeled, stored, and shipped as detailed in the Laboratory Manual.

Participants that are ADA positive at the end of the study and that has more than 2-fold higher titers than at baseline with multiple dosing of AZD8233 will be asked to return to provide another sample after 3 months to evaluate whether or not ADAs persist. If positive ADA-results, and more than 2-fold higher titers than at baseline, subjects will be asked to return after an additional 3 months (i.e., 6 months after the end of study visit). If the sample is ADA positive at 6 months, the Investigator and AstraZeneca Physician will discuss additional actions and decide on future monitoring frequency. If 3 months (and 6months) have already passed at the time AstraZeneca confirmed a participant's sample of Visit 17 for Part A and Part C or Visit 16 for Part B was ADA positive, the investigator will ask the participant to return to the study site as soon as possible to provide ADA sample. Results of ADA at 3 months and 6 months after the end of study will not be recorded in the eCRF module or in the database. Participants with treatment-induced ADAs are considered ADA positive until levels have returned to within 2-fold of baseline or levels have dropped 97% from maximum.

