4.3 Justification for Dose

[Part A]

In the Phase 1 SAD study (Study D7990C00001), which has been conducted in the US, single SC doses of AZD8233 up to **CCI** have been well tolerated in participants with elevated LDL-C.

The dose to be evaluated in Part A is **CCI**.

This is the highest dose that has been evaluated in the MAD study (Study D7990C00002) conducted in the US, and is also the highest planned dose to be evaluated in Part B. A dose of **CCI** monthly is expected to result in close to the maximum achievable reduction in PCSK9 and hence LDL-C levels over the dose interval with AZD8233.

One extra dose (loading dose) is planned to be administered one week after the first dose with the purpose to reach steady state conditions more quickly in trough concentrations (assumed to reflect tissue concentrations). As the loading dose is administered after the initial large decline in plasma concentrations of the first dose, the loading dose is predicted to result in minimally higher C_{max} or AUC_{0-48} as compared to the first single dose. Thus, a total of 4 doses are planned to be administered to each subject, i.e., dosing on Days 1, 8, 29, and 57.

A dose of **CCI** monthly is expected to result in a mean C_{max} and AUC_{0-48} at steady state at approximately half the exposure limits defined from the NOAEL dose in a 3-month toxicity study in cynomolgus monkeys. From a safety perspective, risks observed in other ASO development programs can be divided into acute and chronic risks. Acute risks, as those related to C_{max} , including transient increase in activated partial thromboplastin time (aPTT), are expected to occur very soon after dosing. Chronic risks, like reduction of platelet count and development of ADAs have, if at all, most often appeared after more than 3 months of dosing.

Taken together, the benign safety profile observed for single doses of AZD8233 up to **CCI**

support initiation of Part B after the SRC will review safety data up to 7 days after last dose administration in Part A. Data later than Day 64 (if available) may be reviewed by the SRC as needed.

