4.2.6.1 Definition

Development of anti-drug antibodies (ADA) and ADA titre will be used to evaluate the immunogenicity of AZD8233. Titre evaluations are conducted only on those samples that are confirmed positive for ADA.

Treatment-induced ADA positive is defined as ADA negative at baseline and post-baseline ADA positive.

Treatment-boosted ADA positive is defined as ADA positive at baseline and boosted the pre-existing titre post-baseline (≥ 4 -fold increase).

TE-ADA positive is defined as the sum of treatment-induced ADA positive and treatment-boosted ADA positive.

TE-ADA negative is defined as ADA positive but not fulfilling the definition of TE-ADA positive.

ADA persistently positive is defined as either ADA negative at baseline and ADA positive at ≥ 2 post-baseline assessments (with ≥ 16 weeks between first and last positive) either ADA positive at last post-baseline assessment.

ADA transiently positive is defined as ADA negative at baseline, having at least one postbaseline ADA positive assessment and not fulfilling the conditions of ADA persistently positive.

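### In the Part B SAP, the last-sample route to persistent ADA has no baseline condition, and for anyone first positive on Day 85 or later it is the only route

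*Protocol*

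**What the plan says.** **Part B SAP, 4.2.6.1.** The persistence sentence opens with "ADA persistently positive is defined as either ADA negative at baseline and ADA positive at ≥ 2 post-baseline assessments", asks for at least 16 weeks between the first and last positive, and then offers the alternative "either ADA positive at last post-baseline assessment". The companion rule reads "ADA transiently positive is defined as ADA negative at baseline, having at least one postbaseline ADA positive assessment", and excludes anyone who is persistently positive. A further rule reads "TE-ADA negative is defined as ADA positive but not fulfilling the definition of TE-ADA positive". TE-ADA positive means either a negative baseline with a later positive, or a positive baseline with at least a 4-fold titre rise. Section 4.2.6.4 tabulates all these categories.

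**Protocol Table 2, footnote g.** Part B ADA samples are taken on Days 1, 8, 29, 57, 85, 113 and 141 and at the final visit (Day 169) or early discontinuation visit.

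**Protocol 8.5.2.** Participants who are positive at the end of the study, with titres more than 2-fold above baseline, are asked to "provide another sample after 3 months to evaluate whether or not ADAs persist", and to return again at 6 months if still positive with raised titres. On recording, the section states: "ADA at 3 months and 6 months after the end of study will not be recorded in the eCRF module or in the database". No SAP section uses these later results.

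The persistent and transient categories exist only in the Part B SAP. The Part A and Part C SAPs tabulate ADA positivity and titre without them. The non-recording rule covers all three parts.

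**The concern.** There are two problems in one definition.

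First, the baseline condition is attached to the 16-week limb but not, as written, to the last-sample limb. A category meant to describe how a response to treatment lasts can then take in subjects whose antibodies predate treatment and did not change.

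Second, the two limbs give evidence of different strength under one label. The 16-week limb shows duration. The last-sample limb shows only that the subject was positive when sampling stopped. If late responders can enter only by the second limb, the table does not tell the reader which persistent cases were shown to last and which were merely open at the final visit.

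At stake is the meaning of one descriptive row of a secondary endpoint in a part with about 60 participants. The primary LDL-C analysis is not affected.

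**Working it through.** The plan gives no figure for this point, so there is none to reproduce. The check applies the rules to cases.

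**1. A subject positive at baseline, with the same titre throughout and positive on Day 169**

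| Part B SAP category | Requirement | Met? |
|---|---|---|
| Treatment-induced | Negative baseline | No |
| Treatment-boosted | Titre rise of at least 4-fold | No |
| TE-ADA positive | Either of the above | No |
| TE-ADA negative | ADA positive, not TE-ADA positive | **Yes** |
| Persistent, 16-week limb | Negative baseline | No |
| Persistent, last-sample limb | Positive at last assessment | **Yes** |
| Transient | Negative baseline | No |

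The subject is counted as TE-ADA negative and as persistently positive. As written, baseline-positive subjects can enter the persistent row but never the transient row.

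**2. Longest in-study span by day of first positive**

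The requirement is 16 × 7 = 112 days. The longest span is 169 minus the first positive day.

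| First positive day | Longest span (days) | Can meet 112? |
|---|---|---|
| 8 | 161 | Yes |
| 29 | 140 | Yes |
| 57 | 112 | Exactly |
| 85 | 84 | No |
| 113 | 56 | No |
| 141 | 28 | No |
| 169 | 0 | No |

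The latest qualifying first positive is 169 − 112 = Day 57. With visit windows of ±2 days, a Day 57 first positive spans between 167 − 59 = 108 and 171 − 55 = 116 days, so it can fail. A Day 85 first positive spans at most 171 − 83 = 88 days, so windows do not rescue it.

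**3. Possible patterns for a baseline-negative completer**

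Seven post-baseline samples give 2⁷ − 1 = 127 patterns with at least one positive.

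- Positive on Day 169: 2⁶ = 64, all persistent.
- Of those, first positive on Day 85 or later: 2³ = 8. They are persistent by the last-sample limb alone.
- The other 64 − 8 = 56 also meet the 16-week limb.
- Negative on Day 169 but at least 112 days between positives (Day 141 positive, with Day 8 or Day 29 positive): 3 × 2³ = 24.
- Transient: 127 − 64 − 24 = 39.

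Of the 8 last-limb-only patterns, 7 contain two or more positives and one is a lone positive on Day 169. These are counts of possible patterns, not expected proportions of subjects.

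**4. What the recall samples could add**

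Assume that 3 and 6 months are about 91 and 182 days after Day 169, that is, Days 260 and 351. A positive at 3 months gives spans of 175, 147 and 119 days from first positives on Days 85, 113 and 141. All reach 112, which covers 7 of the 8 patterns. For the lone Day 169 positive the span is 91 days at 3 months (short) and 182 at 6 months (enough). This applies only to participants who are recalled and attend.

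**The case against.** The strongest reply on the baseline condition is that the sentence is garbled rather than wrong. It uses *either* twice, and the transient rule, which is limited to baseline-negative subjects and excludes persistent ones, suggests that the limit was meant for both limbs. Section 4.2.6.4 also has a separate row for subjects positive both at baseline and after it, plus listings and individual titre plots, so these subjects stay visible. That is fair as to intent, but a programmer following the text would misclassify, and the text needs correcting under either reading.

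Several stronger inferences are tempting, and the documents do not support them:

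- *The persistence rate is overstated.* No document gives ADA rates or follow-up results. A last-sample positive may prove lasting, and 4.2.6.2 counts missing ADA results as negative, which can push the other way.
- *The recall samples are collected and then ignored.* Under protocol 8.5.2 the 3-month result decides whether the participant returns at 6 months, and a positive 6-month result prompts discussion of further monitoring. They are used for individual follow-up but kept out of the study database and SAPs.
- *The immunogenicity objective is answered by a proxy.* The Part B endpoint is ADA development and titre during treatment and follow-up, which in-study samples address directly. Persistence is one of ten rows in the 4.2.6.4 list.
- *Late onset is what the protocol expects here.* Protocol 4.3 says of other ASO programmes that "development of ADAs have, if at all, most often appeared after more than 3 months of dosing". Part B gives three doses, the last on Day 57, in an 84-day treatment phase, so that remark does not predict its timing.
- *The label rests on a single sample.* Last-sample positivity is one of two routes, and 7 of the 8 patterns that depend on it contain more than one positive.

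**Conclusion.** The point holds as a defect in a stated classification rule. As written, an unboosted baseline-positive subject who is positive at the last sample is both persistently positive and TE-ADA negative. Separately, a completer first positive on Day 85 or later can reach at most 84 nominal days (88 with windows) against 112, and is called persistent only because Day 169 is positive. For that group persistence is unverified at end of study; the direction of any error is unknown.

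How many subjects this touches cannot be derived from the documents. If no subject is ADA positive at baseline, the first part changes nothing; if no subject is first positive from Day 85 on, neither does the second. The day arithmetic uses the nominal schedule and a subject with all seven post-baseline samples. For early leavers the last assessment can fall well before Day 169. Sections 4.2.6.2 (missing counted as negative) and 4.2.6.3 (missing not imputed) leave unclear whether a missing Day 169 sample counts as the last one.

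**What to change.** **Main change, Part B SAP 4.2.6.1 and 4.2.6.4.** Require ADA negative at baseline for both limbs of the persistence definition. Report subjects who qualify only through the last-sample limb in a separate row, labelled as persistence not established at end of study. The cost is a few lines of SAP text and one table row, with no new data.

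**Optional and secondary.** Give the 3- and 6-month ADA results for recalled participants in a listing or CSR addendum. This contradicts protocol 8.5.2 as it stands, so it needs a protocol amendment with the approvals described in Appendix A 1, as well as a data transfer. The results would arrive after the main report and at irregular times, since 8.5.2 allows late recall. They would cover only participants with titres more than 2-fold above baseline. They should therefore be descriptive and should not redefine the main label.
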